Project title	A Danish Audit of Small Bowel Obstruction	
Participating Centres	Bispebjerg Hospital; Herlev Hospital; Hillerod Hospital; Hvidovre Hospital; Slagelse Hospital; Zealand University Hospital, Køge;	
Principal Investigator	[name] Abdominal Center K, Bispebjerg Hospital [contact]	
Local Investigators	Bispebjerg Hospital	[name] [contact]
	Herlev Hospital	[name] [contact]
	Hillerod Hospital	[name] [contact]
	Hvidovre Hospital	[name] [contact]
	Slagelse Hospital	[name] [contact]
	Zealand University Hospital, Køge	[name] [contact]

1. Background

Small bowel obstruction (SBO) is a common and potentially life-threatening acute surgical condition. A minority of patients present with a clear indication for urgent surgical intervention, either on the basis of clinical or radiological assessment (clinical signs of peritonitis/sepsis; suspicion of bowel ischaemia; closed loop obstructions; irreducible herniae etc.). However, the optimal management of the remaining patients, the majority of whom present with SBO caused by abdominal adhesions, remains a topic of international debate.

In the United Kingdom, the majority of patients with adhesional SBO are managed non-operatively unless a clear indication for acute surgery is found. This approach is based on both the rationale that the acute presentation may resolve with non-operative management and that surgical intervention may lead to the development of further adhesions, leading to further episodes of SBO in the future [1]. The management of adhesional SBO in Denmark is more surgically aggressive, where the majority of patients tend to undergo an acute or urgent operation unless there is a clear contraindication to surgery. The rationale for this approach is that the patient has been admitted with clinically significant adhesions, which will continue to cause intermittent obstruction unless divided. Although there is some evidence to support a more aggressive approach, with a recent retrospective study from Canada demonstrating fewer future episodes of SBO in patients undergoing operative management, the benefit of the acute surgical intervention must be balanced with the risks of peri-operative morbidity [2].

In 2017, a snapshot audit of the outcomes of patients admitted with SBO in the UK was performed, including over 2,400 patients (<https://www.acpgbi.org.uk/content/uploads/2017/12/NASBO-REPORT-2017.pdf>) [3]. This audit not only identified variations in the management of patients with SBO but also identified several key recommendations to improve the outcomes of this patient group including earlier use of CT scanning, a more standardised approach to non-operative management, a greater focus on nutritional status and optimisation of peri- and post-operative care.

Standardised acute care bundles are now commonplace in Denmark. With a focus on early identification of high-risk surgical patients, these pathways facilitate early radiological diagnoses, pre/peri-operative patient optimisation and early, appropriate surgical intervention. Although one of the key patient groups identified by these pathways, the outcomes of patients admitted with SBO are not routinely audited, which limits further optimisation of patient care.

This quality assessment study aims to provide robust data on the outcomes of patients admitted with SBO in Region Øst in order to identify areas in need of improvement and further research.

2. Objectives

To perform a prospective quality assessment study of the outcomes of management of patients admitted with SBO in Region Øst.

Primary objective

- 30-day morbidity and mortality rates of patients admitted with SBO

Secondary objectives

- 90-day mortality rates of patients admitted with SBO
- To identify the most common causes of SBO in this patient cohort
- To investigate potential variability in the diagnosis and peri-operative management of these patients
- To determine what proportion of patients undergo non-operative vs operative management of SBO
- To determine the success rate of non-operative management in patients with SBO and identify predictors of success/failure
- To determine the incidence and consequence of acute kidney injury in patients with SBO
- To determine the incidence and consequence of malnourishment in patients with SBO

Tertiary objectives

- To identify areas of management of patients with SBO requiring optimisation

- To determine the incidence of recurrent SBO at 1-year, 3-year and 5-year follow-up.

3. Methods

This is a prospective quality assessment study that will be performed across 6 acute general surgical hospitals in Region Øst (Bispebjerg, Herlev, Hillerød, Hvidovre, Køge, Slagelse). Consecutive consenting patients admitted with a diagnosis with SBO will be included from each site over a 3-month period.

Eligible patients will be identified using the following methods during the study period:

- Screening of acute theatre lists
- A data extraction of all diagnoses of ileus (DK567) or subileus (DK566C) from the emergency department and inpatient wards
- A data extraction of from the radiology department of all patients undergoing a small bowel follow-through with water soluble contrast

In the initial study phase, each patient will be followed for 90 days after diagnosis. Relevant clinicopathological variables will be extracted from electronic patient records, which will be entered in a pseudo-anonymised form into a purpose-built REDCap database using a site-specific study number that is individual for each patient. Patient CPR numbers will be stored on secure folders at each site to allow data validation as necessary. The first analysis of the dataset will be performed

once all included patients have reached 90 days follow-up. Patient journals will be accessed again at 1, 3 and 5 years after diagnosis to investigate the tertiary objectives outlined above.

As this study is purely observational, no alterations to standard patient care will be made. The study will be run by a steering committee including senior surgeons acting as local principal investigators from each of the participating centres. An additional collaborator from each centre will be responsible for patient identification and data collection. It is estimated that each centre will identify between 20-30 eligible patients each month, giving a final cohort size of 360-540 patients.

4. Patients

Inclusion criteria

- Age \geq 18 years old
- Radiological or clinical diagnosis of mechanical SBO made from 00:00 on 22/02/2021 until 23:59 on 21/05/2021
- Admitted to one of the 6 participating centres

Exclusion criteria

- SBO presenting within 30 days of a previous abdominal operation

5. Risks and side effects of study

This is a prospective observational study of patient outcomes. As such, there are no risks or potential side effects for the patients that will be included.

6. Access to patient journals

Patient journals will be accessed in order to extract relevant clinicopathological data. The local principal investigators are responsible for the relevant study approvals, which should be made as a quality assessment project. As described above, patient journals will be accessed at 4 timepoints during this study:

- Period 1 – from diagnosis until 90 days follow-up
- Period 2 – 1 year after diagnosis
- Period 3 – 3 years after diagnosis
- Period 4 – 5 years after diagnosis

7. Data storage and security

Patient identifiable data will be stored in a secure folder at each specific site. The local principal investigators will be responsible for establishing and maintaining these folders. Only those directly involved with the study will have access to these files. Relevant clinicopathological variables will be entered into a purpose-built REDCap database in an anonymised form. Each site will have a specific REDCap login with site-specific patient study numbers.

Any patient identifiable data will be permanently deleted within 5 years of the study start (i.e. 31/12/2026).

8. Publication of results

This study is registered on www.clinicaltrials.gov – NCT04750811. The results of the study will be published in scientific journals and presented at international conferences.

9. References

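### Does pooling all small bowel obstruction in the operative versus non-operative proportion answer the wrong question?

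*Protocol*

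**What the plan says.** The Background (section 1) divides SBO in two. "A minority of patients present with a clear indication for urgent surgical intervention"; for everyone else, it says, "the optimal management of the remaining patients, the majority of whom present with SBO caused by abdominal adhesions, remains a topic of international debate". It then contrasts two national practices in adhesional SBO. In the United Kingdom, "the majority of patients with adhesional SBO are managed non-operatively unless a clear indication for acute surgery is found". Danish practice is described as more surgical, "where the majority of patients tend to undergo an acute or urgent operation unless there is a clear contraindication to surgery".

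Section 2 states the overall aim: "To perform a prospective quality assessment study of the outcomes of management of patients admitted with SBO in Region Øst". Among the secondary objectives is "To determine what proportion of patients undergo non-operative vs operative management of SBO". Identifying the most common causes of SBO is another.

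Section 4 admits adults with a "Radiological or clinical diagnosis of mechanical SBO made from 00:00 on 22/02/2021 until 23:59 on 21/05/2021" at one of the six centres. The only exclusion is SBO arising within 30 days of an abdominal operation. Patients who need urgent surgery are therefore in the denominator, whatever the cause.

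**The concern.** The Background appears to set up a question about one group, and the objective then measures another. Patients with peritonitis, ischaemia, a closed loop or an irreducible hernia would be expected to have surgery under either national approach. Counting them raises the operative share without saying anything about the debated choice.

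The stake would be a misreading. A pooled operative share above 50% might be taken to confirm that most Danish adhesional patients are operated on, even if most patients without an urgent indication were managed non-operatively. Recurrence at 1, 3 and 5 years looks open to the same mixing, because a repaired hernia and divided adhesions are counted together.

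**Working it through.** **Cohort size.** The only calculated figure in the protocol reproduces: 6 centres × 3 months × 20 = 360, and 6 × 3 × 30 = 540. Near 50%, the 95% half-width 1.96 × √(0.25/n) is 5.2 points at n = 360 and 4.2 points at n = 540.

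**Inputs for the mixing argument.** The protocol gives no urgent share and no operative share, so every value below is an assumption. Let u be the urgent share, r the operative share among urgent patients, and q the operative share among the rest. The pooled share is P = u·r + (1 − u)·q, and its excess over q is u·(r − q).

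**Step 1: pooled against non-urgent.** With r = 1 and q = 0.40:

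| u | P | Excess over q |
|---|---|---|
| 0.10 | 0.46 | 6 points |
| 0.20 | 0.52 | 12 points |
| 0.30 | 0.58 | 18 points |

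The pooled and non-urgent shares therefore differ, by more than the sampling error at n = 360.

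**Step 2: crossing 50%.** With r = 1, P exceeds 0.5 while q is below 0.5 only if q lies between (0.5 − u)/(1 − u) and 0.5. That band is 0.444–0.5 at u = 0.1, 0.375–0.5 at u = 0.2 and 0.286–0.5 at u = 0.3. If q is above 0.5, both shares lie on the same side: at u = 0.2, q = 0.6 gives P = 0.2 + 0.8 × 0.6 = 0.68. A crossing thus needs a non-urgent share below one half. An assumed range of 50–70% for that share, which fits the Background's description of Denmark, produces none.

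**Step 3: pooled against adhesional.** Adhesional and non-urgent are different groups. The Background says only that most of the remaining patients are adhesional, and an adhesional obstruction can itself be urgent. Take u = 0.2, r = 1, with 60% of non-urgent and 20% of urgent patients adhesional. Adhesional patients are then 0.2 × 0.2 + 0.8 × 0.6 = 0.52 of the cohort.

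- *Operative share 0.60 in non-urgent adhesional and 0.10 in non-urgent non-adhesional patients:* P = 0.2 + 0.8 × (0.6 × 0.6 + 0.4 × 0.1) = 0.52. Among all adhesional patients the share is (0.04 + 0.8 × 0.6 × 0.6)/0.52 = 0.63. The pooled share is lower than both 0.60 and 0.63.
- *Operative share 0.40 in both non-urgent groups:* P = 0.2 + 0.8 × 0.4 = 0.52. Among all adhesional patients it is (0.04 + 0.8 × 0.6 × 0.4)/0.52 = 0.446. The pooled share is higher than both 0.40 and 0.446.

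The same pooled 52% can overstate or understate the adhesional share. The protocol does not fix the direction.

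**Step 4: the Background's practice statements.** The sentence on Danish practice concerns adhesional SBO and makes an exception only for contraindications to surgery. The exception for an acute surgical indication is in the United Kingdom sentence. A figure restricted to adhesional patients without an urgent indication would therefore not match the Danish statement either. It would also be less precise: if 60% of non-urgent patients are adhesional, n = 360 × 0.8 × 0.6 ≈ 173 at u = 0.2 and 360 × 0.7 × 0.6 ≈ 151 at u = 0.3, with half-widths of about 7.5 and 8.0 points.

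**The case for a change.** The best case for the concern rests on comparisons between sites. Section 2 also aims to explore variability in diagnosis and peri-operative management. Two hospitals with the same non-urgent practice (q = 0.40, r = 1) but urgent shares of 10% and 30% would show pooled shares of 46% and 58%, a 12-point gap from case mix alone. A larger cohort would not shrink it. Urgency at diagnosis is also not named as a variable, and recording it later, with the operation already known, would be less clean.

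The arithmetic stands, and so does its lesson: the pooled share should not be read as the non-urgent or the adhesional share. But the protocol does not say that raw pooled shares will be compared between hospitals, and case-mix handling is ordinary analysis-plan content. Cause of SBO is needed for a stated objective, so a split by cause is already possible. Section 3 refers only to relevant clinicopathological variables, and the data form is not part of the document, so one cannot say that urgency is missing from it. The recurrence objective asks for incidence alone and specifies no comparison by treatment.

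**Conclusion.** The concern does not hold. The aim is to describe the management and outcomes of all patients admitted with SBO, and the all-patient operative share is the correct quantity for it. The account of Danish practice is context: the protocol attaches no test, hypothesis or threshold to it, so the objective carries no conclusion that pooling could reverse.

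What is true is limited. The pooled share exceeds the non-urgent share by u·(r − q), which is 6 to 18 points for assumed u of 10–30%, r = 1 and q = 40%. It crosses the 50% line only if the non-urgent share is below one half, contrary to what the Background expects. Against the adhesional share the direction is undetermined. All of these sizes rest on assumed values.

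Also reporting the share and recurrence by cause and urgency would be a sensible addition, but a statistical analysis plan would commonly provide for it and none is at hand. Followed as written, this objective gives a sound descriptive result.

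### Section 3 limits inclusion to consenting patients, but the section 4 criteria, the primary objective and the cohort estimate carry no consent condition; if the filter is applied, 30-day outcomes may be biased

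*Protocol*

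**What the plan says.** The inclusion rule is in section 3 (Methods): "Consecutive consenting patients admitted with a diagnosis with SBO will be included from each site over a 3-month period".

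Other parts of the protocol define or count the cohort without that restriction:

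- Section 2, primary objective: "30-day morbidity and mortality rates of patients admitted with SBO".
- Section 4, inclusion criteria: adult age, a diagnosis of mechanical SBO within the study window, and "Admitted to one of the 6 participating centres".
- Section 4, the only exclusion: "SBO presenting within 30 days of a previous abdominal operation".
- Section 3, cohort size: "It is estimated that each centre will identify between 20-30 eligible patients each month, giving a final cohort size of 360-540 patients".

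Section 3 finds eligible patients from theatre lists and from diagnosis-code and radiology extractions. Data collection is also records-based: "Relevant clinicopathological variables will be extracted from electronic patient records". Section 6 makes the local principal investigators responsible for approvals, to be sought on a quality-assessment basis.

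**The concern.** Who enters the cohort sets the denominator of the primary outcome, and the protocol gives two answers. One site could include everyone who meets section 4, and another only those who agreed. Both could claim to follow the protocol, and approvals are handled locally, so such a divergence is possible in practice.

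The outcome makes this matter. Section 1 opens: "Small bowel obstruction (SBO) is a common and potentially life-threatening acute surgical condition". The primary objective is what happens within 30 days. A patient who dies soon after admission, or who is too ill to be asked, may never become a consenting patient. If the filter is applied literally, the chance of being included can depend on the outcome being measured. The audit would then describe a somewhat healthier group than the patients admitted with SBO whom the objective names.

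**Working it through.** **1. The plan's own figure.** Inputs from section 3: 6 centres, 3 months, 20-30 eligible patients per centre per month.

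- 6 x 3 x 20 = 360
- 6 x 3 x 30 = 540

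The stated range is reproduced exactly. It is a count of eligible patients, but the protocol calls it the final cohort. No factor for non-consent enters.

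**2. The range with an allowance for consent.** The protocol gives no consent rate, so these fractions are assumptions.

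| Consent | Included patients |
|---|---|
| 100% | 360-540 |
| 90% | 324-486 |
| 80% | 288-432 |
| 70% | 252-378 |

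The loss of precision is small. The 95% half-width is 1.96 x sqrt(p(1-p)/n). At an assumed mortality of 8% it is 2.80 points at n = 360 and 2.29 at n = 540. At 80% consent it becomes 3.13 (n = 288) and 2.56 (n = 432).

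**3. Possible bias.** Let m be the true event rate, and let cd and cs be the fractions included among patients with and without the event. Then:

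- observed rate = m x cd / (m x cd + (1 - m) x cs)
- included n = N x (m x cd + (1 - m) x cs), with N = 360 or 540 eligible

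All rates are assumed. For mortality, m = 8%:

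- cs = 0.9, cd = 0.5: 0.040 / (0.040 + 0.828) = 4.6%, a shift of -3.4 points. The half-width at the included n is 3.0 (N = 360) or 2.5 (N = 540), so the bias exceeds sampling error.
- cs = 0.9, cd = 0.7: 0.056 / (0.056 + 0.828) = 6.3%, a shift of -1.7 points against 3.0 or 2.4. The bias is within sampling error.
- cs = cd = 0.9: 8.0%, no bias.
- cs = 0.8, cd = 0.9: 0.072 / (0.072 + 0.736) = 8.9%, a shift of +0.9 points against 3.1 or 2.6. The bias is within sampling error.

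For morbidity, m = 30%:

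- cs = 0.9, cd = 0.5: 0.15 / (0.15 + 0.63) = 19.2%, a shift of -10.8 points against 5.4 or 4.4.
- cs = 0.9, cd = 0.7: 0.21 / (0.21 + 0.63) = 25.0%, a shift of -5.0 points. This exceeds the half-width at 540 eligible (4.2) but not at 360 (5.2).

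The effect therefore depends on how strongly inclusion differs by outcome. It is nil when inclusion is equal and material when the difference is large. The document cannot say which case applies.

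**The case against.** The strongest reply is that the word is a stray. Patients are found by extraction, data come from records, approval is sought as quality assessment, the criteria omit consent, and the cohort estimate equals all eligible patients. On that reading no filter operates and no bias arises. This is quite possible, and it is why the point is conditional on the filter being applied. But the word stands in the inclusion rule, and a site that follows it literally is not in error.

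A second reply is that section 4 may define who is eligible and section 3 who among them is included, so the two need not conflict. Even so, the objective speaks of all patients admitted with SBO, and the eligible count is still labelled as the final cohort. Consent pages may also be absent from the public text. The point does not rest on a missing form or procedure.

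Two stronger readings are tempting but not supported:

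- A reader might infer that the 360-540 range holds only at 100% consent. Only its exact endpoints need that. With 25 eligible patients per centre per month, 6 x 3 x 25 = 450, and 80% of 450 is 360, still inside the range. The range is an estimate, and no power or precision target in the protocol rests on it.
- A reader might infer from section 1 ("A minority of patients present with a clear indication for urgent surgical intervention") that only a small share could be affected. An urgent surgical indication is not a measure of inability to consent, and the protocol does not link the two.

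It also stands that every rate in the bias illustration is assumed, and that most of the mortality cases shown stay within sampling error.

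**Conclusion.** The point holds in a conditional form. The consent restriction in section 3 is not matched by section 4 or by the primary objective, and the cohort estimate makes no allowance for it. If the filter is applied as written, 30-day mortality and morbidity may be biased. Downward is the most plausible direction, because early death and severe illness are the obvious obstacles to consent; this is a judgement, not something the protocol establishes.

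The size cannot be derived from the document. The fall from 8% to 4.6% shows what a strong imbalance would do, with the mortality and both inclusion fractions assumed. The effect on precision is minor. The matter deserves correction because it touches the denominator of the primary outcome and is cheap to settle.

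**What to change.** **Where the quality-assessment approvals permit inclusion without consent:** delete *consenting* from section 3 and state that all consecutive patients who meet the section 4 criteria are included. The objective, the criteria and the 360-540 estimate then agree.

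**Where consent is required:**

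- add it to the section 4 criteria;
- state how patients who die or lack capacity before being asked are handled, with their record data included where the approvals allow;
- label 360-540 as the expected number of eligible patients rather than the final cohort;
- report the number eligible and the number included at each site.

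The counts show how much selection is possible but do not measure the bias. The handling of patients who cannot be asked is what limits it.

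**Cost:** a check of each site's approval and a few lines of text. If consent stays, there is also a per-site count, drawn from screening that is already planned, and possibly a smaller stated cohort.

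### Does tying case-finding to an undefined study period lose eligible patients diagnosed just before 21/05/2021?

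*Protocol*

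**What the plan says.** Section 4 (Inclusion criteria) sets the window by diagnosis: "Radiological or clinical diagnosis of mechanical SBO made from 00:00 on 22/02/2021 until 23:59 on 21/05/2021". Section 3 describes accrual as "Consecutive consenting patients admitted with a diagnosis with SBO will be included from each site over a 3-month period" and then introduces the search: "Eligible patients will be identified using the following methods during the study period".

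Three routes follow in section 3:
- "Screening of acute theatre lists";
- "A data extraction of all diagnoses of ileus (DK567) or subileus (DK566C) from the emergency department and inpatient wards";
- a radiology extraction of "all patients undergoing a small bowel follow-through with water soluble contrast".

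On timing after inclusion, section 3 adds: "In the initial study phase, each patient will be followed for 90 days after diagnosis". The first analysis waits until all patients have reached that point, and records are reopened at 1, 3 and 5 years.

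The protocol does not define the study period. Nor does it say which date each search selects on, when the extractions are run, or when searching ends.

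**The concern.** Eligibility depends on one date and case-finding on others. An operation or contrast study normally falls at or after diagnosis, and a code cannot sensibly precede it. If the study period means the 3-month inclusion window, someone diagnosed on 19/05/2021 whose first marker is dated 24/05/2021 is eligible but lies outside the search. Nothing offsets this at the start of the window, because diagnoses before 22/02/2021 are ineligible.

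The cohort would then not be consecutive in its last days, and the chance of being missed would rise with the delay to the first marker. If long delays go with bad outcomes, for example late failure of non-operative treatment, the 30-day morbidity rate would be biased downwards. The secondary objective on success or failure of non-operative management would lose some of its failures.

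**Working it through.** **Inputs from the protocol.** Six centres, 3 months, 20 to 30 patients per centre per month (section 3); diagnosis window 22/02/2021 to 21/05/2021 (section 4).

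**The plan's own figure.** 6 × 3 × 20 = 360 and 6 × 3 × 30 = 540, which reproduces the stated cohort size. The window is 89 days, so 360/89 = 4.0 to 540/89 = 6.1 diagnoses per day across all sites.

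**Loss if every search closed on 21/05/2021.** With uniform accrual, share lost = f × L / 89. Here f is the share of patients whose first marker in any route comes after diagnosis, and L is their mean lag in days. Neither is in the protocol, so both are assumed.

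| f | L (days) | Share lost | Patients lost (of 360 to 540) |
|---|---|---|---|
| 0.10 | 2 | 0.10 × 2/89 = 0.2% | about 1 |
| 0.25 | 5 | 0.25 × 5/89 = 1.4% | 5 to 8 |
| 0.50 | 7 | 0.50 × 7/89 = 3.9% | 14 to 21 |
| 1.00 | 10 | 1.00 × 10/89 = 11.2% | 40 to 61 |

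The last row needs every patient to have no marker in any route until 10 days, on average, after diagnosis.

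**Bias in the 30-day rate.** Assume 20% of patients have long courses with a 50% event risk, and the rest a 10% risk. True rate = 0.2 × 0.5 + 0.8 × 0.1 = 18.0%. All patients are taken to depend on the late marker.
- Lags 14 and 3 days: retained weights are 0.2 × (1 − 14/89) = 0.1685 and 0.8 × (1 − 3/89) = 0.7730. Observed rate = (0.1685 × 0.5 + 0.7730 × 0.1) / 0.9416 = 17.2%.
- Lags 20 and 1 day: weights are 0.1551 and 0.7910. Observed rate = (0.1551 × 0.5 + 0.7910 × 0.1) / 0.9461 = 16.6%.

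The 95% half-width at 18% is 1.96 × √(0.18 × 0.82/n): 4.0 points at n = 360 and 3.2 at n = 540. The shifts are 0.8 and 1.4 points.

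**A harsher set of assumptions.** Take true morbidity of 30% and exponential delays with mean 5 days if uncomplicated and 15 if complicated. Share lost = (d/89) × (1 − exp(−89/d)), giving 0.0562 and 0.1681. If a fraction q of patients depends on the late marker, observed morbidity = 0.3(1 − 0.1681q) / [0.3(1 − 0.1681q) + 0.7(1 − 0.0562q)]. This is 27.4% at q = 1, 28.8% at q = 0.5 and 29.4% at q = 0.25.

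**Does the text impose the strict reading?** No sentence ends the search on 21/05/2021. Section 3 treats the 90 days after diagnosis as part of the initial study phase, and section 6 counts record access up to 5 years as part of the study. Two of the three routes are extractions of stored records. Run after 21/05/2021 and selected on diagnosis or admission date, they would lose no one for reasons of timing.

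**The case for a change.** The strongest case for a change is that the 3-month reading is the natural one. The preceding sentence in section 3 names a 3-month period, follow-up has its own label, and the accrual estimate counts patients identified per month over three months. Six centres, each with its own collaborator, might close their searches on different dates in a study that looks at variability in diagnosis and management. Any resulting bias would not average out, the confidence interval would not show it, and a longer search costs little because the first analysis already waits for day 90.

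Part of this stands. The term is undefined, the short reading is plausible, and a bias smaller than the sampling error is still a bias. Three things limit its weight.
- A patient must escape every route. Codes are taken from the emergency department as well as the wards, and may be assigned at presentation, though the protocol does not give coding times.
- The direction is not established. Section 1 describes Danish practice as mostly acute or urgent surgery, and section 2's opening text describes pathways built for early imaging and operation. Patients with peritonitis or ischaemia would reach a theatre list early, and a post-operative complication cannot delay the operation that preceded it. Selective loss needs late non-operative failure, or coding only at discharge, with no earlier marker.
- The loss is not irrecoverable while the extractions can still be re-run before the 90-day analysis.

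A formal 90-day run-out would also raise its own question: section 3 includes consenting patients, and some of those found late would have been discharged or have died.

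**Conclusion.** The concern does not call for a change. The protocol leaves the search dates unspecified; it does not set a rule that drops eligible patients. Inclusion is defined by diagnosis date and meant to be consecutive, so the sensible way to fill the gap is to capture everyone diagnosed from 22/02/2021 to 21/05/2021, whatever the date of the operation, contrast study or code, before the first analysis. Done that way, the loss from this cause is nil and the planned 360 to 540 is unaffected.

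If a site did stop on the last day, the loss would be about 1 to 4% under moderate assumptions. Even when every patient is taken to depend on a delayed marker, the 18.0% illustration moves by 0.8 to 1.4 points, against a half-width of 3.2 to 4.0. These sizes rest on assumed delays, uniform accrual and an assumed link between delay and outcome. The larger figures (11.2% lost, or 30% observed as 27.4%) require every patient to depend on a late marker, which fits poorly with the early diagnosis and surgery that the protocol describes. The descriptive conclusions on 30-day morbidity and mortality would stand either way.
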